## 13. Data & Safety Monitoring Committee

A Data & Safety Monitoring Committee (DSMC) will be established for this study. The DSMC will be independent from the Sponsor and the study investigators. It will consist of at least three (3) members: two interventional cardiologist physicians that will also act on the CEC and an independent statistician; the two physicians must have extensive experience with large-bore cardiovascular interventions, preferably experience using the MANTA VCD. The DSMC will be established and operate according to a charter defined prior to the initiation of the trial. The DSMC will review cumulative adverse event data and will recommend study termination if safety

concerns warrant such action. If the DSMC believes it is possible to predict adverse events, guideline criteria for recommending study termination will be established before enrollment in the study begins. The DSMC will meet by phone or face-to-face, at least 2 times during the study in order to assure close and timely monitoring of adverse events and outcomes.

## 14. Risks and Benefits

### 14.1. Anticipated Clinical Benefits

There are no guaranteed benefits from participation in this study. The MANTA VCD is FDA approved and has received CE Mark in Europe, allowing the device to be marketed in the United States and Europe. The MANTA VCD is investigational in Canada. In published clinical studies, the MANTA VCD has shown to be safe and effective in closing large bore arteriotomies with low rates of vascular complications.

The U/S technique used for closure is not currently part of the approved labeling for the MANTA VCD but has been used at some hospitals as part of standard practice. It is thought that U/S closure may decrease rates of vascular complications in patients whose access sites are closed with the MANTA VCD.

Information gained from this study may be used to benefit future MANTA patients and help guide their therapy.

### 14.2. Anticipated Risks

#### 14.2.1. *Risks of Study Required Assessments*

Data collected for this study includes mostly standard of care assessments. Assessments that may be specific to this protocol include additional U/S evaluations at the time of the closure procedure.

The U/S evaluations are noninvasive and do not expose subjects to harmful radiation. There are no risks associated with this test, and most people feel little to no discomfort during use of U/S.

#### 14.2.2. *Anticipated Adverse Device Effects*

Use of the U/S-guided MANTA VCD deployment carries risk from procedural error, inherent use hazards, and device failure. This method does not pose any new or increased risks compared to using the MANTA VCD without U/S. A complete list of anticipated adverse device effects can be found in Section 11.2 - Potential Adverse Events and Adverse Device Effects.

#### 14.2.3. *Risk Mitigation*

Clinical risks will be minimized by careful assessment of the subject prior to, during, and after the procedure. Careful follow-up will help minimize risks associated with changing conditions of the subject. Subjects will be selected in accordance with the subject inclusion and exclusion criteria.

All Investigators selected to participate will have performed at least 25 successful cases with a MANTA VCD and have currently used U/S for access in at least 50 large bore procedures. Additionally, prior to enrolling in the study, all investigators will have completed formal training and documented up to 2 roll-in cases.

The study sites selected will have adequate personnel, resources and facilities to safely conduct the study in compliance with this protocol and the study agreement.

#### **14.2.4. Risk to Benefit Rationale**

The potential benefits of U/S-guided MANTA VCD closure are expected to outweigh the aforementioned mitigated risks and exceed or meet the performance of current treatment methods, and the study itself carries almost no additional risk. Therefore, the clinical study is justified by the risk/benefit ratio.

### **15. Statistical Analysis**

#### **15.1. Study Hypothesis**

##### **15.1.1. Safety**

The primary safety analysis will be performed on the first 75 chronologically enrolled PAC (non roll-in) subjects where an attempt to use the MANTA VCD is made (enrolled subjects without an attempt will not be included). In addition, all Adverse Events recorded during the study will be summarized, and severity and relatedness to the device and/or procedure will be reported. Roll-in subjects will be analyzed separately from the PAC. The primary safety endpoint is any Large Bore Access-site Related VARC-2 Major Vascular complication (LBAR VARC-2 Major) within 30 days as defined in Section 6 and adjudicated by the CEC.

The primary safety hypothesis is that the LBAR VARC-2 Major complication rate (proportion of subjects with one or more) is less than the Performance Goal of 14.2%, as follows:

$$H_0: \pi \geq 0.142$$

vs.

$$H_A: \pi < 0.142,$$

where  $\pi$  is the population LBAR VARC-2 Major complication rate within 30 days.

The primary safety hypothesis is that the rate of LBAR VARC-2 Major complications within 30 days of the procedure is less than the performance goal of 14.2%. Derivation of the performance goal is described below.

Stated in words, the hypothesis is:

Null hypothesis: The rate of LBAR VARC-2 Major complications within 30 days after the procedure is not less than the performance goal of 14.2%

Alternate hypothesis: The rate of LBAR VARC-2 Major complications within 30 days after the procedure is less than the performance goal of 14.2%

#### **15.2. Sample Size Considerations**

The performance goal and the postulated event rate in the prospective study population are based upon clinical judgment supported by outcomes from comparable published studies in Table 4 below; in particular rows pertaining to studies of similar size to the proposed 75 patients are shown in bold. Results for all studies shown used VARC-2 definitions.

Table 4: Safety Performance of the MANTA VCD from Published Literature

Reference	N MANTA VCD subjects	VARC-2 Major Complication			95% Confidence Interval*
		Essential Medical Sponsored	Independent MANTA VCD Studies	Overall	
Van Mieghem 2017 (CE Mark)	50	2.0%		2.0%	0.0%, 10.6%
Wood 2019 (IDE Study) 	263	4.2%		4.2%	2.1%, 7.4%
Van Mieghem 2020 (MARVEL) 	500	4.0%		4.0%	2.5%, 6.1%
Biancari 2018	107		9.3%	9.3%	4.6%, 16.5%
DePalma 2018	89		1.1%	1.1%	0.0%, 6.1%
Gheorghe 2019 	169		0.6%	0.6%	0.0%, 3.3%
Hoffman 2018	75		10.7%	10.7%	4.7%, 19.9%
Moccetti 2019	100		7.0%	7.0%	2.8%, 13.9%
Moriyama 2019	111		7.0%	7.0%	3.2%, 13.7%
Van Wiechen 2021	102		1.9%	1.9%	0.2%, 6.9%
Moccetti 2021	100		1.0%	1.0%	0.2%, 5.4%
Weighted Average	1666	3.9%	4.4%	4.2%	2.0, 8.4%

\* CI's were estimated from reported VARC-2 performance using exact binomial methods

Based on these results, the population LBAR VARC-2 Major complication rate is hypothesized to be 4.2%, the weighted average of the above rates. Examining the confidence intervals above, the upper confidence limits for comparably-sized studies range from 5.4% to 19.9%, corresponding to point estimates of 1.0% to 10.7%. A performance goal of 14.2%, which is based on clinical judgment regarding device performance, falls well within this range, indicating that it is constructed in a fashion consistent with prior findings in the literature.

Additionally, though Sponsor does not intend to demonstrate better safety outcomes than with use of the current approved procedure, determining deployment depth of MANTA using the depth locator, the value of 14.2% is more stringent than the performance goal of 19.9% which was accepted for the MANTA VCD PMA study.

Using these inputs, a one-sided alpha of 0.025 and at least 80% power, 69 subjects will provide adequate power to reject the primary safety hypothesis. To ensure an adequate sample size of subjects meeting the 30-day primary safety endpoint, and to account for patient attrition, data from the first 75 consecutive subjects (with a maximum of 15 subjects at any one site to cap enrollment at 20% of subjects enrolled per site) in the PAC will be analyzed and submitted as to support a PMA supplement for revised labeling to include the U/S-guided method.

Additional subjects will be enrolled as part of the PAC to provide supplementary data in support of future publications for a total of 150 enrolled subjects (with a maximum of 30 subjects at any one site and/or PI to cap enrollment at 20% of subjects enrolled per site) in the overall study.

Additionally, roll-in subjects (up to 2 per operator per site) using the MANTA VCD will be enrolled to allow investigators to learn how to use the U/S-guided therapy with the MANTA VCD. This group will be analyzed separately and not count towards the PAC.

### **15.3. Data Analysis**

#### **15.3.1. *Cohort Definitions***

**Primary Analysis Cohort (PAC):** Subjects in the PAC that have had an attempt to use the MANTA VCD with use of U/S to guide placement. The first 75 consecutively enrolled subjects of this cohort will be submitted as a PMA supplement. A total of 150 subjects will make up the total PAC.

**Roll-in Cohort:** Additionally, up to 2 roll-in subjects per operator using the MANTA VCD will be enrolled to allow investigators to learn how to use the U/S-guided therapy with the MANTA VCD. Roll-in subjects will not count towards the 150 subjects making up the PAC.

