### **7.6. Enrollment**

All subjects that sign an informed consent, undergo the TAVR procedure, and an attempt (insertion of MANTA VCD sheath) to close the arteriotomy with the MANTA VCD will be considered enrolled and will be followed until study conclusion. If a subject signs the informed consent, but does not undergo the TAVR procedure or if no attempt is made to use the MANTA device, the subject will be withdrawn from the study and will not count toward total population analyzed.

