### **11.3. Adverse Event (AE) Assessment**

Starting at the time an attempt is first made to use the MANTA VCD (including U/S use post TAVR valve deployment and prior to MANTA VCD use) and at each subsequent evaluation, the investigator will determine if any AEs have occurred in any subject. Subjects are encouraged to report AEs freely or in response to general, non-directed questioning. The subject may volunteer information that appears to be an AE anytime during the study. If an AE is determined to have occurred, the investigator should obtain all the required information and document findings on the eCRF.

In general, a primary diagnosis for the event should be reported instead of each symptom. Only exacerbated conditions or new onset qualify as an AE, but if patient history is in question, report AE conservatively.

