### 11.6. AE and Serious Adverse Event (SAE) Reporting to Sponsor

All SAEs, irrespective of potential causal relationship to the device, procedure or study, that occur from the point of attempted MANTA VCD placement (including U/S use post TAVR completion and prior to MANTA VCD use) onwards will be reported to the Sponsor within 24

hours of the Investigator's first knowledge of the event. Suspected SAEs also should be reported.

The Investigator will forward information, via the eCRF system, about an SAE promptly, even if the information is incomplete or it is obvious that more data will be needed to form any conclusions. This information will be available to the Sponsor and CRO in the database. Additional information regarding the SAE will be recorded on the follow-up AE form forwarded to the Sponsor.

All AEs should be reported on the eCRF as soon as practicably possible. AEs will be recorded by their final medical diagnosis and not by each separate symptom. The information for the event will include the date of awareness, onset and resolution, the action taken, the corrective treatment and how the subject recovered with or without sequelae. In case of death, the relationship of death to the investigational device and/or the study procedure will be well documented. The date on which subject expired, what attempts were made to treat the event that led to death, the performance and functioning of the device during the event will be noted.

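### The PAC definition adds an ultrasound-guidance condition that the enrolment rule and the primary-analysis text lack, so an enrolled subject whose guidance is abandoned can be left out of the primary test

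*Protocol*

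**What the plan says.** **Enrolment (Protocol 7.6).** A subject who consents, undergoes TAVR and has "an attempt (insertion of MANTA VCD sheath) to close the arteriotomy with the MANTA VCD will be considered enrolled", and is then followed to the end of the study. If there is no TAVR or no attempt, "the subject will be withdrawn from the study and will not count toward total population analyzed".

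**Cohort definition (Protocol 15.3.1, repeated in SAP 6.1).** The PAC is "Subjects in the PAC that have had an attempt to use the MANTA VCD with use of U/S to guide placement". The sentence is circular, since it defines the PAC by reference to subjects in the PAC. It also adds an ultrasound condition.

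**Primary analysis (Protocol 15.1.1).** The test uses the first 75 chronologically enrolled PAC subjects, with PAC explained in brackets only as non-roll-in, and specifies "subjects where an attempt to use the MANTA VCD is made (enrolled subjects without an attempt will not be included". SAP 6.3 says the same of an Analysis Cohort, a term that SAP 6.1 does not define. SAP 8 likewise makes a procedure attempt the only condition for being summarised. None of these three places mentions ultrasound.

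**Adverse event collection (Protocol 11.3).** Assessment starts when "an attempt is first made to use the MANTA VCD (including U/S use post TAVR valve deployment and prior to MANTA VCD use". Section 11.6 starts SAE reporting at the same point.

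**Success rule (Protocol 15.3.2).** The exact one-sided upper 97.5% bound must be below 14.2%.

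**The concern.** Whether ultrasound guided the placement is settled only at closure, after the sheath is in and the subject is already enrolled under 7.6. A condition of that kind should not decide membership of the primary set. If guidance is abandoned and closure is finished another way, 7.6, 15.1.1, SAP 6.3 and SAP 8 keep the subject. Protocol 15.3.1 and SAP 6.1 can be read to drop the subject. Since the roll-in cohort is not open to that subject either, he or she could be enrolled and belong to no cohort.

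The study is meant to show that ultrasound-guided closure is safe and to support revised labelling. Cases in which guidance breaks down are part of that question. The study is unblinded and has no control arm, so a choice made with outcomes visible is not offset by the same choice in a comparator. If abandoned cases have more complications than the rest, dropping them lowers the estimated rate.

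**Working it through.** **1. The passages applied to three kinds of non-roll-in subject**

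| Subject | 7.6 | 15.1.1, SAP 6.3, SAP 8 | 15.3.1, SAP 6.1 |
|---|---|---|---|
| Sheath inserted, ultrasound guidance completed | enrolled, followed | in | in |
| Sheath inserted, guidance abandoned, closure finished another way | enrolled, followed | in | in or out, depending on the reading |
| Ultrasound for closure begun, abandoned before sheath insertion | withdrawn, not counted | out | out |

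The conflict over the analysis set is in the second row. The third row is handled consistently, but under 11.3 such a subject may already have reportable adverse events, and neither document says where they are shown. Protocol 15.1.1 also excludes enrolled subjects without an attempt. Under 7.6 that group is empty, because enrolment requires an attempt.

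**2. The plan's sample size**

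Inputs from Protocol 15.2: event rate 4.2%, performance goal 14.2%, one-sided alpha 0.025, power at least 80%. For each n, take c as the largest x with P(X ≤ x | n, 0.142) ≤ 0.025. Power is P(X ≤ c | n, 0.042).

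- n = 68: c = 3, power 68.0%.
- n = 69: c = 4, exact alpha 0.0248, power 83.6%.

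The smallest n reaching 80% is 69, so the plan's figure reproduces.

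**3. The pass limit at 75**

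The exact upper bound is U(x, n) = the 0.975 quantile of Beta(x + 1, n − x).

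| Events / subjects | Upper bound | Result against 14.2% |
|---|---|---|
| 4/75 | 13.10% | pass |
| 5/75 | 14.88% | fail |
| 4/74 (one subject with an event dropped from 5/75) | 13.27% | pass |

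If the dropped subject is replaced by the next enrolled subject, who has no event, 5/75 becomes 4/75, which also passes.

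**4. How often dropping would change the verdict**

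The documents give no frequency or event rate for abandoned guidance, so these inputs are assumptions: k = 1 to 4 abandoned cases among 75, event rate q = 10 to 20% in them, and r = 4.2 to 7% in the others. All k are taken to be dropped without replacement. The limit is 4 events for every n from 71 to 75. The verdict changes when the others have at most 4 events but the total is 5 or more:

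P(change) = Σ (x = 0 to 4) P(X = x | 75 − k, r) × P(Y ≥ 5 − x | k, q)

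| k | q | r = 4.2% | r = 6% | r = 7% |
|---|---|---|---|---|
| 1 | 10% | 1.8% | 2.0% | 1.7% |
| 1 | 20% | 3.6% | 3.9% | 3.4% |
| 2 | 10% | 3.6% | 3.9% | 3.5% |
| 2 | 20% | 7.2% | 7.8% | 6.8% |
| 4 | 10% | 7.2% | 7.9% | 7.0% |
| 4 | 20% | 14.9% | 15.4% | 13.4% |

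The range is about 2% to 15%. The expected number of events removed is k × q, from 1 × 0.10 = 0.1 to 4 × 0.20 = 0.8.

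**5. Effect on a false pass**

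Suppose the true rate over all subjects is exactly 14.2%. With everyone counted, the chance of passing at n = 75 is 1.3%. If abandoned cases are dropped and replaced, assuming they are 2 to 10% of subjects with an event rate of 15 to 50%, the chance is 1.4% to 10.7%. Over the combinations tried (2, 5 and 10% of subjects; event rates of 15, 30 and 50%), it exceeds 2.5% only for 5% of subjects at a 50% event rate, and for 10% at 30% or 50%.

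**The case against.** The strongest case for the plan is that 7.6 gives attempt a clear operational meaning, sheath insertion, and that 15.1.1, SAP 6.3 and SAP 8 can all be read with it. On that reading, failed guidance after insertion removes nobody. The PAC sentence asks for an attempt with ultrasound, not for successful guidance, so a subject in whom ultrasound was tried and failed can still satisfy it. This stands: the text permits dropping the subject and does not require it. What remains is the discretion, because nothing in either document fixes which reading applies.

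A reader might infer four stronger points, which the documents do not support.

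- That there are three rival analysis sets, one starting at ultrasound use. Sections 11.3 and 11.6 only time the collection of adverse events and SAEs. They define no analysis set.
- That the rate is biased downward. This needs abandoned cases to have a higher event rate than the rest, which the documents do not show. With a lower rate, dropping them would raise the estimate.
- That subjects abandoned before sheath insertion must be in the primary set. Section 7.6 withdraws them expressly. Counting a subject who never had a MANTA sheath is a choice of estimand, not the correction of an error.
- That the probability of exactly 5 events (11.2% at a true rate of 4.2%) measures the harm. That is the chance of landing one event above the limit. The chance of a changed verdict is the one in the table above.

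Exclusion 20 narrows the problem but does not close it. It removes subjects whose anatomy cannot be seen clearly at initial access, not those in whom guidance fails at closure. The closure steps are in site-binder instructions that were not available for this review. They may make abandonment rare, but they would not normally define the analysis set.

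**Conclusion.** The point holds as an inconsistency that should be settled before analysis. Protocol 15.3.1 and SAP 6.1 carry a condition, known only at closure, that 7.6, 15.1.1, SAP 6.3 and SAP 8 do not. It leaves open whether an enrolled subject with abandoned ultrasound guidance is in the primary test.

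The downward bias is possible but not established. Its likely size is small: 0.1 to 0.8 events, with a 2 to 15% chance of changing the verdict. The upper end requires 4 of 75 cases at a 20% event rate, all dropped. These figures rest on assumed frequencies and rates. What needs no assumption is that the pass limit lies between 4 and 5 events, so a single classification can decide the outcome. Priority: should be changed. Confidence: medium.

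**What to change.** Use one definition in Protocol 7.6, 15.1.1 and 15.3.1 and in SAP 6.1 and 6.3. The primary set is the first 75 non-roll-in subjects with MANTA sheath insertion in whom ultrasound-guided closure was intended, kept in the analysis whether or not ultrasound guidance or deployment was completed. The existing per-site cap is unaffected. Remove the circular wording and the reference to enrolled subjects without an attempt, and use one cohort name in the SAP.

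Then add:

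- a sensitivity analysis of the subset completed as intended;
- a listing of consented subjects withdrawn under 7.6 after ultrasound for closure began but before sheath insertion, with any adverse events collected under 11.3;
- a sensitivity analysis that counts those subjects, stating how far each was followed.

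The cost is wording in both documents, one listing and two supplementary analyses. Because 7.6 ends follow-up for the withdrawn subjects, a complete 30-day count would need their 30-day status, which should concern few people. The performance goal, alpha and planned sample size do not change. The downside for the sponsor is a rate that may be slightly less favourable.

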#### **15.3.2. *Primary Safety Endpoint***

The rate of LBAR VARC-2 Major complications within 30 days (based on CEC-adjudicated data) following procedure will be presented along with the exact one-sided upper 97.5% confidence bound for subjects with one or more events. If this upper confidence bound is less than 14.2%, the study will have met its primary objective.

#### **15.3.3. *Secondary Endpoints***

Secondary endpoints will be summarized using descriptive statistics including mean, standard deviation, median, range for continuous data and frequency and proportions for categorical data.

The following secondary endpoints will be evaluated for the MANTA VCD, definitions are provided in Section 6.

- Time to Hemostasis (effectiveness)
- Technical Success (effectiveness)
- Ambulation Success (effectiveness)
- Time to Ambulation (effectiveness)
- Treatment Success (effectiveness)
- Procedure Time (effectiveness)
- Any Large Bore Access-site Related VARC-2 Minor Vascular (LBAR VARC-2 Minor) complication within 30 days (based on CEC-adjudicated data) (safety)

#### **15.3.4. *Additional Analyses***

The following outcomes will be analyzed using descriptive statistics:

- Any long-term LBAR VARC-2 Major and Minor complications (>30 days to 12 months post procedure)
- Procedural and Post-procedural Characteristics such as:
  - Readmission rates within 30 days
  - Delayed ambulation (beyond institution's ambulation protocol) for subjects

with LBAR VARC-2 Major or LBAR VARC-2 Minor complications

- Delayed discharge (beyond institution's discharge protocol) for subjects with LBAR VARC-2 Major or LBAR VARC-2 Minor complications
- Use of adjunctive devices required at large bore access site (Angio-Seal, ProGlide, Prostar XL, balloon, stent, covered stent or surgical repair)
- VARC-3 Major and Minor Vascular Complications within 30 days (adapted from VARC-3 criteria)
- Subsequent Secondary Intervention(s) (For example, any new surgical or percutaneous interventions post the index large bore procedure that occurred on the femoral artery of the MANTA (ipsilateral) leg, such as percutaneous coronary intervention (PCI), through the 12 month follow-up phone call.)

